7.2.2 Functional/Global Assessments

Functional Activities Questionnaire (FAQ): The FAQ is an inventory of instrumental activities of daily living developed by ([Pfeffer 1982](#)). The FAQ is administered by asking the informant to rate patient's ability (0-3) on 10 different activities of daily living. The total FAQ score ranges from 0 to 30, with higher scores indicating greater functional loss. The FAQ will be administered according to the Schedule of Activities in Table 1 and Table 2.

Amsterdam-Instrumental Activities of Daily Living Questionnaire (A-IADL): The A-IADL is an adaptive questionnaire designed to assess impairments in instrumental activities of daily living in early dementia. ([Sikkes 2013](#)) The questionnaire is completed by a caregiver / informant. The original questionnaire consists of 70 items in seven categories and the administration time is approximately 20-25 minutes. The A-IADL total score is calculated using an item response theory method of scoring and lower scores indicate greater functional impairment. The A-IADL will be administered according to the Schedule of Activities in Table 1 and Table 2.

Clinical Dementia Rating Scale (CDR): The CDR scale is used as a global measure of dementia and is completed by a clinician in the setting of detailed knowledge of the individual patient collected from interviews with the caregiver (first) and patient

(second).[\(Berg, 1988\)](#) The CDR describes 5 degrees of impairment in performance on each of 6 categories including memory, orientation, judgment and problem solving, community affairs, home and hobbies, and personal care. The interview takes approximately 40 minutes to administer.

CDR global ratings are 0 for cognitively unimpaired individuals, 0.5 for questionable dementia and 1, 2 and 3 for mild, moderate and severe dementia as defined in the CDR scale. The scores for each category can also be summed and this is known as the sum of box score (CDR-SB). Sum of box scores range from 0 to 18 with higher scores indicating greater cognitive impairment.

The CDR will be administered according to the Schedule of Activities in [Table 1](#) and [Table 2](#) and the subject must in a fed state.

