9.0 DATA ANALYSIS/STATISTICAL METHODS

The statistical considerations summarized in this section describe the protocol-defined plan for data analysis of this study. A final and complete Statistical Analysis Plan (SAP) will be finalized prior to unblinding the data from the learning stage of the study (Part 1), possibly updated prior to unblinding the confirmatory stage of the study (Part 2). The SAP will supersede the protocol. Any deviations from the planned analyses will be described and justified in the final integrated study report.

This trial describes two studies (learning stage and confirming stage) with a common infrastructure in a single protocol. Statistical analysis of the clinical efficacy variables will be done for each of the study studies separately. Analysis of MRI volumetric data only applies to part 2 of the study. Statistical evaluation of adverse events will be done by each part separately and also integrated for the study as a whole. Statistical analysis of safety measures that are collected by visit will be done for the study as a whole (combined).

Continuous variables will be presented showing number of observations available, mean, median, minimum, maximum, 1st and 3rd quartiles, and standard deviations (or standard errors, depending on the variable) by visit. Categorical variables will be presented showing frequencies and percentages by visit.

All tests will be 2-sided and use an overall study-wise $\alpha = 0.05$ unless otherwise stated. SAS Version 9.4 or later will be used. Medical dictionary for Regulatory Activities (MedDRA) Version 21.0 or later will be used for coding adverse events. Medications will be coded using WHO Drug Dictionary (WHODD) Version March 2018 or later.

This study features a conditional sequential approach to hypothesis testing to control alpha, similar to methods using Bauer closed procedures.

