1.10 Adaptive Study

This study is an adaptive trial, which includes 2 studies under the same protocol. This SAP is focused on Part 1 of this adaptive study.

This SAP conforms to standards set forth in *Adaptive Designs for Clinical Trials of Drugs and Biologics Guidance for Industry* (CDER, CBER, November 2019). The intention of the adaptive nature of this protocol is to leverage potential advantages related to statistical analysis as depicted in the FDA final guidance.

2 Statistical Hypotheses

Part 1 has a single primary endpoint (ADAS-Cog14).

The testing sequence will be as follows for strict significance, however proof of concept will be attained by significance in any of the outcomes below (Figure 1):

The first set of hypotheses to be tested is as follows:

H₀₁: The mean change in ADAS-cog14 in the active group is equal to that of the placebo group*.

H₁₁: The mean change in ADAS-cog14 in the active group is not equal (is superior) to that of the placebo group*.

Conditional on statistical significance, testing will proceed hierarchically:

H₀₂: The mean change in A-IADL in the active group is equal to that of the placebo group.

H₁₂: The mean change in A-IADL in the active group is not equal (is superior) to that of the placebo group[§].

Conditional on statistical significance, testing will proceed:

H₀₃: The mean change in CDR-sb in the active group is equal to that of the placebo group.

H₁₃: The mean change in CDR-sb in the active group is not equal (is superior) to that of the placebo group[§].

Conditional on statistical significance, testing will proceed:

H₀₄: The mean change in FAQ in the active group is equal to that of the placebo group.

H₁₄: The mean change in FAQ in the active group is not equal (is superior) to that of the placebo group[§].

H₀₅: The mean change in the cognitive composites or GST in the active group is equal to that of the placebo group.

H₁₅: The mean change in the cognitive composites or GST in the active group is not equal (is superior) to that of the placebo group.

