5.1.5 Efficacy Scales

Generation of instrument total scores will be calculated from individual items. The following instruments that are used in this study are subject to statistical analysis:

5.1.5.1 Alzheimer's Disease Assessment Scale - Cognitive Subscale 90 point (ADAS-cog):

- Range: The scale range is 0 to 90 with higher scores indicating greater cognitive impairment.
- Brief description: The 14-Item Alzheimer's Disease Assessment Scale - Cognitive Subscale (ADAS-cog14) is a structured scale (approximately 45 minutes to complete) that evaluates memory, orientation, attention, reasoning, language, constructional praxis, delayed recall, digit cancellation, and maze-completion. The ADAS-cog14 scoring range is from 0 to 90, with higher scores indicating greater cognitive impairment (Mohs et al. 1997). The ADAS-Cog should always be administered prior to other cognitive measures. The ADAS-Cog will be administered at Screening, Baseline, Months 3 and 6 or in the event of early termination. Participants must have scores of ≥ 10 at Screening and Baseline to be eligible for participation in the study.

5.1.5.2 Mini Mental State Examination (MMSE):

- Range: The scale range is 0 to 30 with lower scores indicating greater cognitive impairment.
- Brief description: The MMSE is a brief 30-point test that is used to assess cognition (Folstein, 1975). It is commonly used to screen for dementia. In the time span of about 10 minutes, it samples various functions, including arithmetic, memory and orientation. The MMSE will be administered at Screening, Baseline, Months 3 and 6 or in the event of early termination. Participants must have scores of 21-26 at Screening and 19-27 at Baseline to be eligible for participation in the study.

5.1.5.3 Functional Activities Questionnaire (FAQ):

- Range: The score ranges from 0 to 30. Higher scores are associated with greater impairment.
- Brief description: The FAQ is an inventory of instrumental activities of daily living developed by (Pfeffer 1982). The FAQ is administered by asking the informant to rate patient's ability (0-3) on 10 different activities of daily living. The FAQ will be administered at Screening, Baseline, Months 3 and 6 or in the event of early termination.

5.1.5.4 Amsterdam-Instrumental Activities of Daily Living Questionnaire (A-IADL):

- Range: scoring range from 20 to 80, with lower scores indicating greater impairment.

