- Brief description: The A-IADL is an adaptive questionnaire designed to assess impairments in instrumental activities of daily living in early dementia.(Sikkes 2013) The questionnaire is completed by a caregiver / informant. The original questionnaire consists of 70 items in seven categories and the administration time is approximately 20-25

minutes. The A-IADL total score is calculated using an item response theory method of scoring (Embretson and Reise 2000, Reise and Waller). Higher scores indicate greater functional impairment. The A-IADL will be administered at Screening, Baseline, Months 3 and 6 or in the event of early termination.

5.1.5.5 Clinical Dementia Rating Scale (CDR):

- Global CDR Range:
 - 0 = normal; healthy individuals
 - 0.5 = questionable dementia
 - 1 = mild dementia
 - 2 = moderate dementia
 - 3 = severe dementia.

- CDR sum-of-boxes (CDR-sb) range:

CDR-sb scores range from 0 to 18 with higher scores indicating greater cognitive impairment.

- Brief description: The CDR scale is used as a global measure of dementia and is completed by a clinician in the setting of detailed knowledge of the individual patient collected from interviews with the patient and caregiver (Berg, 1988). The CDR describes 5 degrees of impairment in performance on each of 6 categories including memory, orientation, judgment and problem solving, community affairs, home and hobbies, and personal care. Much of the information will therefore already have been gathered, either as part of normal clinical practice or as part of a research study. The interview takes approximately 40 minutes to administer.

The scores for each category can also be summed and this is known as the sum of box score (CSR-SB). The CDR will be conducted at Baseline and at Months 3 and 6 or in the event of early termination. To avoid patient fatigue, the CDR may be performed on a separate, but proximate, visit day than the other cognitive tests.

5.1.5.6 Global Statistical Test (GST):

A GST allows assessment of a global change in disease status/trajectory by standardizing and then combining measures. The GST will be a combination of 3 z-scores (ADAS-COG, CDR-SB, and A-IADL) with standardization calculated using the baseline mean and standard deviation for each score. The GST will be calculated for each subject at each timepoint by averaging the three z-scores and this GST will then be analyzed as a new outcome by calculating change from baseline to each visit.

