8.1 Definition of Baseline

For safety evaluations, the Baseline assessment for all measurements will be the latest available, valid measurement taken prior to the initiation study medication, except for electrocardiography (ECG) values: The Baseline assessment for ECG include a triplicate assessment with the baseline value intended to be the arithmetic mean of the values taken at the Baseline assessment that are taken in triplicate. Baseline values for efficacy outcomes will be the average of screening and baseline visits where available. For the GST, the z-scores at each visit will be calculated using the mean over all patients of the average of screening and baseline, and using the standard deviation pooled across screening and baseline.

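### The GST averages three z-scores with no sign rule while the SAP contradicts itself on A-IADL direction, so functional benefit may count against the drug and functional harm for it

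*SAP*

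**What the plan says.** SAP 5.1.5.6 standardises ADAS-cog, CDR-sb and A-IADL and combines them: "The GST will be calculated for each subject at each timepoint by averaging the three z-scores". SAP 8.1 adds only the reference values: "For the GST, the z-scores at each visit will be calculated using the mean over all patients of the average of screening and baseline", with a standard deviation pooled over the same two visits. Neither section reverses a component or says which GST direction is favourable.

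SAP 5.1.5 scores ADAS-cog14 (0 to 90) and CDR-sb (0 to 18) so that higher is worse. On A-IADL there are three statements:

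- SAP 5.1.5.4, range line: "scoring range from 20 to 80, with lower scores indicating greater impairment".
- SAP 5.1.5.4, description: "Higher scores indicate greater functional impairment".
- Protocol 7.2.2: "lower scores indicate greater functional impairment".

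Protocol 9.0 says "The SAP will supersede the protocol", so the conflict inside the SAP has to be settled in the SAP.

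On the role of the GST, SAP section 2 says that "proof of concept will be attained by significance in any of the outcomes below", and the GST is in the last hypothesis on that list. SAP 5.1.4 brings it in when ADAS-cog is not significant and makes no correction for it. The A-IADL alternative reads "The mean change in A-IADL in the active group is not equal (is superior) to that of the placebo group", without a direction.

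**The concern.** A global test of this kind works only if all its components point the same way. The SAP's averaging rule is right under one of its two A-IADL statements and wrong under the other. Two programmers could each follow the SAP, one reversing A-IADL and one not, and produce different endpoints. Settling the matter after unblinding would be a data-dependent choice.

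If lower A-IADL is worse, the average as written is cognition plus global rating minus functional impairment. Functional benefit then offsets cognitive benefit, and functional harm adds to it. This matters because the GST can deliver the Part 1 conclusion by itself. That route is likely to be used: SAP 1.6 gives ADAS-cog only 30% power at 43 patients.

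**Working it through.** **Sign algebra (needs no assumption on effect size or correlation).** Take lower A-IADL as worse, and let negative change mean benefit on ADAS-cog and CDR-sb. Compare GST = (z_ADAS + z_CDR + z_AIADL)/3 as written with the version in which z_AIADL is multiplied by -1. Illustrative changes of 0.3 SD:

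| Scenario | As written | Aligned |
|---|---|---|
| Benefit on all three | (-0.3 - 0.3 + 0.3)/3 = -0.10 | (-0.3 - 0.3 - 0.3)/3 = -0.30 |
| Functional benefit only | +0.3/3 = +0.10 | -0.3/3 = -0.10 |
| ADAS-cog and CDR-sb benefit, functional harm | (-0.3 - 0.3 - 0.3)/3 = -0.30 | (-0.3 - 0.3 + 0.3)/3 = -0.10 |

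Computing every z-score as mean minus score, instead of score minus mean, does not help: all three signs flip and A-IADL still opposes the other two. If higher A-IADL is worse, the average as written is already aligned.

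**Anchor.** The documents give no effect or power for the GST, so there is no stated GST figure to reproduce. The nearest is ADAS-cog in SAP 1.6: effect 1.54, SD 3.4, so d = 1.54/3.4 = 0.453. A two-sided t-test with 21 v 22 patients, 41 df and alpha 0.05 gives 30.5% power and an expected p of 0.145, against 30% and 0.144 stated.

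**Illustrative power.** Assumptions: lower A-IADL is worse; a benefit of d = 0.453 SD on ADAS-cog and CDR-sb and of k × d on A-IADL; unit-variance change scores with common correlation r; 21 v 22; alpha 0.0499 (SAP 6.6).

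- Aligned: mean (2 + k)d/3, variance (3 + 6r)/9.
- Unreversed: mean (2 - k)d/3, variance (3 - 2r)/9.
- Share of the mean effect kept: (2 - k)/(2 + k), which is 100% at k = 0, 60% at 0.5, 33% at 1, 14% at 1.5 and 0% at 2.

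For example, with k = 1 and r = 0.1 the standardised effect is 0.453/√(3.6/9) = 0.716 aligned and (0.453/3)/√(2.8/9) = 0.271 unreversed. Power from the noncentral t, aligned v unreversed:

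| k | r = 0.1 | r = 0.3 | r = 0.5 |
|---|---|---|---|
| 1 | 63% v 14% | 51% v 16% | 43% v 18% |
| 0.5 | 48% v 25.5% | 38% v 29% | 32% v 34% |
| 0 | 33% v 41% | 26% v 46% | 22% v 54% |

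**Harm case.** No effect on ADAS-cog or CDR-sb, A-IADL worse on drug; only significance in the drug's favour is counted (nominal 2.5%), r from 0.1 to 0.5:

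- Harm of 0.453 SD: 14% to 17% of trials unreversed, 0.3% to 0.5% aligned.
- Harm of 0.8 SD: 33% to 44% unreversed, about 0.1% aligned.

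**Limits.** The SAP standardises by baseline SD, which is not given, and analyses the GST in its risk-adjusted model with last z-score carried forward, not by t-test. If the ratio of change SD to baseline SD for A-IADL is half or twice that of the other scales, with equal effects per change SD, the share kept at k = 1 becomes (2 - 0.5)/(2 + 0.5) = 60% or (2 - 2)/(2 + 2) = 0% instead of 33%.

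**The case against.** The strongest reply is that this is an omission in a secondary place. The SAP describes the GST as a measure of global change, which implies aligned components, and a competent programmer would reverse A-IADL. Two of the three statements agree, so the third looks like a drafting slip. SAP 1.9 confines its precedence to the protocol's statistical section, and protocol 9.11 sends questionnaire scoring to the developers' published guidelines, so the direction of the scale can be found elsewhere. The hypothesis schematic (Figure 1) and the table shells are not available here and might contain a rule. ADAS-cog, CDR-sb and A-IADL are also analysed separately, so functional harm behind a GST success would be visible. Finally, the power figures carry an ADAS-cog11 effect over to CDR-sb, and the harm case needs no CDR-sb effect at all although that scale has functional items.

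Much of this is fair. An unseen rule cannot be excluded, the percentages are illustrations, and the wording of the A-IADL hypothesis needs little once the direction is settled. But none of it supplies a sign step. Intent does not fix the computation when the SAP's own description of the scale tells the programmer that no reversal is needed. Separate analyses would reveal the problem but would not stop the GST from formally meeting the proof-of-concept rule.

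**Conclusion.** The concern holds and should be fixed before unblinding. The readable SAP gives an averaging rule without orientation and contradicts itself on the one component whose orientation matters. The sign error is conditional on lower A-IADL being worse, as the SAP range line and the protocol say; it depends on no assumed effect size. Under that condition, equal standardised benefit on all three scales keeps one third of the intended mean effect.

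The effect on power depends on assumption and does not always run one way: with a small A-IADL effect and correlated scales, the unreversed score can have more power, because it partly measures the contrast between function and the other two. Type I error under a global null is unaffected. What is lost is interpretation: a significant GST could not be read as global benefit, nor a null one as its absence.

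**What to change.** Before unblinding:

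1. Confirm the direction of the A-IADL score as actually delivered, and reconcile both lines of SAP 5.1.5.4 and protocol 7.2.2 with it.
2. Add to SAP 5.1.5.6 and 8.1: *Each z-score is oriented so that higher means worse before averaging; the A-IADL z-score is multiplied by -1 if lower A-IADL scores indicate greater impairment.*
3. In SAP section 2, state the favourable direction for A-IADL and for the GST.

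The cost is a few lines of text and one sign in the code. Step 1 must come first: a reversal applied to a score that already runs higher-is-worse would create the same error. The conditional wording in step 2 guards against that.

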1.6 Sample Size and Power Considerations

Original Sample size considerations for Part 1 (from protocol):

Assuming a standard deviation of the change from Baseline to Month 6 in ADAS-cog14 of 4, using $\alpha = 0.05$, a total sample size of approximately 82 subjects in balanced allocation (41 subjects per group) provides at least 90% power to detect a difference between treatment groups of 2.9 using a 2-sided, 2-sample t-test. Assuming a dropout rate of 18% or less, randomization of 100 subjects provides adequate statistical power for Part 1 to demonstrate superiority of azeliragon over placebo based on the ADAS-cog14. (Section 9.2).

Recalculated power considerations for Part 1:

ADAS-Cog: Estimates and standard deviations were drawn from a model that fit change in ADAS-Cog11 over time using the data from the STEADFAST A-study and B-study combined (N=880). The model utilized all individuals in the study. Estimates were drawn at an HbA1C of 7.2 (average from present TTP488-305 study; Part 1). The estimates of standard deviation and effect size for the change from baseline in ADAS-Cog was 3.4 and -1.54 respectively. Given a sample size of 43, a two-sided α of 0.05 would result in 30% power to detect a significant effect. If we observe the estimated effect size and standard deviation at the given sample size in Part 1 of the current study (TTP-305) we would expect to observe a p-value of 0.144 which could be considered evidence of a trend.

Previous studies (Siemers et al 2016) suggest that mean to standard deviation ratio between ADAS-Cog 11 and 14 are similar, therefore it is expected that the estimates drawn using ADAS-Cog11 will be applicable to ADAS-Cog14 data.

Cognitive Composite: The association of treatment was also tested using a composite that was derived from STEADFAST A and B studies. Composites allow the global assessment of multiple aspects of disease as well as exclusion of items that do not contribute to progression and thus add noise to the data. The composite is composed of the ADAS-Cog comprehension, word finding difficulty, and remembering test instructions variables. The composite will be calculated by summing the within visit z-scores for each item across individuals. Z-scores are calculated by subtracting the individual item score at visit x from the baseline mean item score and dividing this value by the item standard deviation at baseline.

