The ADAS-Cog variables included in the model were chosen using PLS regression where treatment status at 6 months was the outcome variable and ADAS-Cog 11 and CDR-SB individual items were predictor variables. The PLS was modeled using

STEADFAST study B as this dataset showed a smaller ADAS-Cog effect with treatment.

PLS estimates and standard deviations were drawn from the STEADFAST data (A-study and B-study combined) as above for ADAS-cog. The model fit change in PLS over time with estimates drawn at an HbA1C of 7.2. The estimates of standard deviation and effect size for the change from baseline were -0.92 and 1.5, respectively. Given a sample size of 43, an alpha of 0.05 would result in 49% power to detect a significant effect. If we observe the estimated effect size and sd at the given sample size in the present study (Part 1) we would expect to observe a p-value of 0.052 indicating that the composite is somewhat more sensitive to treatment effects than the ADAS-cog 11.

Modified Cognitive Composite: The STEADFAST analysis indicates that a portion of the observed change may be due to age-related cognitive decline. To assess this, a modified composite that incorporated aspects associated with cognitive decline due to aging, specifically trail making test (TMT A/B) and Controlled Oral Word Association Test (COWAT) was generated. As these variables are not available in ELEVAAGE, historic data (ADNI) was used to identify the best surrogate for each. All surrogates were found to be within ADAS-Cog individual items. Word finding difficulty was found to be a suitable surrogate for TMTA, while delayed word recall and ideational praxis were surrogates for TMTB ($r=0.5$, 0.6 , and 0.6 respectively). The COWAT surrogates were orientation and word recognition ($r=0.5$ at 12 months). (delayed recall, ideational praxis, orientation, and word recognition).

The model fit change in PLS over time with estimates drawn at an HbA1C of 7.2. The estimates of standard deviation and effect size for the change from baseline were -1.73 and 2.9, respectively. Given a sample size of 43, a two-sided alpha of 0.05 would result in 47% power to detect a significant effect. If we observe the estimated effect size and sd at the given sample size in the present study (Part 1) we would expect to observe a p-value of 0.059 indicating that the composite is somewhat more sensitive to treatment effects than the ADAS-cog 11.

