* ADAS-Cog will also be run using LZCF. If neither of these are significant, the cognitive composites and global statistical test (GST) will be assessed for significance to demonstrate proof of concept. It is acknowledged that the present study is underpowered to replicate the clinically meaningful effect size observed in the STEADFAST combined A- and B-study diabetes subgroup. Therefore, if the observed effect size (treatment difference) or percent slowing (treatment difference divided by the placebo change) is equal to or greater than the corresponding values from the STEADFAST pooled analysis (-0.92; -61%), this will be considered proof of concept. Lack of strict statistical significance is expected with this range of effect size due to the small n, but this result, in the context of the consistency of the effect seen in STEADFAST Part A with the STEADFAST Part B data would provide proof of concept for this compound.

§ All secondary variables will also be run using LZCF.

3 Estimand Specification

This SAP is constructed to conform to regulatory guidance. In particular, this section is included as recommended by ICH E9 (R1) Addendum on estimands and sensitivity analysis in clinical trials to the guideline on statistical principles for clinical trials (30 August 2017).

In accordance with ICH E9 Addendum, the specification of the estimand is included in this SAP with the 4 attributes detailed in ICH E9 Addendum, Section A.3.1:

- A. The Population, that is, the subjects targeted by the scientific question:
For this study, the population consists of subjects with AD and HbA1c of 6.5% - 9.5% who meet eligibility requirements for the study, receive double-blind medication, and have at least one valid post-baseline measure of ADAS-cog(14).
- B. The variable (or endpoint) to be obtained for each patient, that is required to address the scientific question:
For this study, the primary endpoint is Change in ADAS-cog(14).
- C. The specification of how to account for intercurrent events to reflect the scientific question of interest:
Due to the small sample size intercurrent events will not be accounted for in this analysis.
- D. The population-level summary for the variable that provides, as required, a basis for a comparison between treatment conditions:
For this study, the population-level summary for the variable is the least-squares mean (LSM) of the treatment difference in mean change from baseline in ADAS-cog(14).

4 Populations of Analysis

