5.1.4 Proof of Concept

- Mean change from baseline in Cognitive Composite at Month 6
- Mean change from baseline in Modified Cognitive Composite at Month 6
- Mean change from baseline in GST at Month 6

*If the ADAS-Cog is not significant ($P > 0.05$) the cognitive composites and global statistical test (GST) will be assessed for significance to demonstrate proof of concept. No correction will be performed for these comparisons since they are all testing the overall effect of treatment on progression of disease and are expected to be highly correlated.

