5.1.5.7 Cognitive Composite:

Composites allow the global assessment of multiple aspects of disease as well as exclusion of items that do not contribute to progression and thus add noise to the data. The cognitive composite is composed of the ADAS-Cog comprehension, word finding

difficulty, and remembering test instructions variables. The composite will be calculated at each timepoint by summing the within visit z-scores for each item across individuals. Z-scores are calculated by subtracting the individual item score at visit x from the mean item score at visit x and dividing this value by the item standard deviation at visit x.

5.1.5.8 Modified Cognitive Composite:

The modified composite incorporates the cognitive composite variables as well as aspects associated with cognitive decline due to aging, specifically trail making test (TMT A/B) and Controlled Oral Word Association Test (COWAT). As these variables are not available in ELEVAGE; historic data (ADNI) was used to identify the best surrogate for each. All surrogates were found to be within ADAS-Cog individual items. Word finding difficulty was found to be a suitable surrogate for TMTA, while delayed word recall and ideational praxis were surrogates for TMTB ($r=0.5$, 0.6 , and 0.6 respectively). The COWAT surrogates were orientation and word recognition ($r=0.5$ at 12 months).

5.1.5.9 Biomarker:

Blood for plasma biomarkers will be collected at baseline as well as months 3, 6, and follow-up.

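### The SAP scales the cognitive composite in two incompatible ways, and on the same-visit scaling of 5.1.5.7 its percent slowing cannot tell benefit from harm

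*SAP*

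**What the plan says.** - SAP 5.1.5.7 (Cognitive Composite) gives this rule for item z-scores: "subtracting the individual item score at visit x from the mean item score at visit x and dividing this value by the item standard deviation". The SD is also that of visit x, and the z-scores are summed over three ADAS-Cog items.
- SAP 1.6, for the same three items, gives a different rule: "subtracting the individual item score at visit x from the baseline mean item score and dividing this value by the item standard deviation at baseline".
- SAP 5.1.5.8 (Modified Cognitive Composite) gives no standardisation. The GST in 5.1.5.6 and 8.1 is scaled on baseline.
- SAP 5.1.4 lists change in both composites at Month 6 as proof-of-concept variables. It makes no multiplicity correction because "they are all testing the overall effect of treatment on progression of disease".
- The asterisked footnote to SAP Section 2 also accepts proof of concept if the effect size or "percent slowing (treatment difference divided by the placebo change) is equal to or greater than the corresponding values from the STEADFAST pooled analysis". The values given are -0.92 and -61%. The footnote does not name the outcome to which they belong.
- SAP 1.6 says of the composite: "The estimates of standard deviation and effect size for the change from baseline were -0.92 and 1.5, respectively". The ADAS-Cog effect in the same section is -1.54.
- SAP 6.7 runs the composites only with last z-score carried forward (LZCF). SAP 6.6 scales a carried-forward value as (x - mean)/SD, using the mean and SD of the missed visit.

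**The concern.** The two definitions give different endpoints. The protocol does not settle the matter, because the SAP added the composite (SAP 1.9). Left open, the choice could be made after results are seen.

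Same-visit scaling re-centres the whole sample at each visit, so the average decline from baseline to Month 6 disappears. A ratio with the placebo change as its denominator then loses its meaning. Either limb of the footnote is enough for proof of concept, so a limb that is met regardless of drug effect would decide the question by itself.

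Direction is a second problem. Both definitions subtract the score from the mean, so a higher z-score means better performance. That is opposite to the formula in 6.6 and to a benchmark in which a negative difference is benefit.

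**Working it through.** **1. The SAP's own figure.** Inputs from SAP 1.6: N = 43, two-sided alpha 0.05, and -0.92 and 1.5, whose labels are swapped in the text (an SD cannot be negative). Read -0.92 as the effect and 1.5 as the SD, with arms of 22 and 21.

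- t = 0.92 / (1.5 × √(1/22 + 1/21)) = 0.92 / 0.458 = 2.01.
- Noncentral-t power is 50.1% and p = 0.051. With 21 per arm they are 49.2% and 0.054.
- The SAP states: "Given a sample size of 43, an alpha of 0.05 would result in 49% power to detect a significant effect", and "we would expect to observe a p-value of 0.052". The figures reproduce.

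**2. The identity.** Let A and P be the mean composite changes in the active and placebo arms. Pooled same-visit z-scores sum to zero at every visit, so with complete data nA·A + nP·P = 0, hence A = -P·nP/nA and

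(A - P)/P = -(1 + nP/nA).

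- Equal arms: -200%. For 22 active and 21 placebo: -(1 + 21/22) = -195.5%. For 21 and 22: -(1 + 22/21) = -205%.
- Harmful drug, higher = worse, 22/21: A = +0.20 gives P = -0.2095, and (0.20 + 0.2095)/(-0.2095) = -1.955.
- Helpful drug: A = -0.20 gives P = +0.2095, and the ratio is again -1.955.

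Reversing the subtraction order changes the sign of A - P and of P together, so the ratio is unaffected. The -0.92 limb does reverse.

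**3. Simulation (22/21, 1,500 runs per cell).** The documents do not give these inputs, so they are assumptions: placebo worsening of 0.5 raw units per item, item SD about 1, drug effect of -0.3, 0 or +0.3 per item, z-scores pooled over arms. The table shows the share of runs at or below -61%.

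| Scaling, estimate, dropout | Helps | No effect | Harms |
|---|---|---|---|
| Same-visit, raw means, 0% | 100% | 100% | 100% |
| Same-visit, least squares, 0% | 99% | 97% | 99% |
| Same-visit, raw means, 18% with LZCF | 86% | 69% | 88% |
| Same-visit, least squares, 18% with LZCF | 90% | 73% | 90% |
| Baseline, least squares, 0% | 49% | 0.8% | 0% |
| Baseline, least squares, 18%, carried forward on the baseline scale | 48% | 1.3% | 0% |

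Least squares means an ordinary fit of the SAP 6.2 fixed effects. The random slope and intercept model did not converge reliably and is not used. With dropout and no drug effect, the raw-mean ratio had median -123% and a 5th to 95th percentile range of -834% to +475%. Varying the assumed decline from 0.2 to 1.0, at 18% dropout, gave 52–72% for no effect and 81–91% for harm.

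A separate simulation with slower decline (0.2–0.5 SD per item) and 0–18% dropout put the baseline-scaled rates at 1–28% for an inert drug and 0–8% for a harmful one. Baseline scaling therefore restores discrimination but does not make the ratio precise.

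**4. Where the benchmark came from.** If -61% is percent slowing, the placebo change is 0.92/0.61 ≈ 1.5. Pooled same-visit sample means at 1:1 would instead give 0.92/2 = 0.46 and -200%. But 0.92/1.5 = 0.61 as well, so -61% also equals effect divided by SD, and its derivation needs checking.

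**The case against.** The strongest reply is that the criterion named for the composites, in the footnote and in 5.1.4, is statistical significance, and that same-visit scaling leaves this usable. That stands. A check with complete data, 22/21 and assumed inputs (decline 0.35 SD per item, inter-item correlation 0.3) compared a t-test on change under the two scalings:

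- Inert drug: rejection in 5.1% of runs same-visit against 5.5% baseline-scaled.
- Benefit of 0.5 SD per item: power 51% against 58%.
- Harm of 0.3 SD per item: false benefit in at most 0.1% on either scaling.
- The -0.92 limb, same-visit: met in 7% of inert and 0.4% of harmful trials.

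A reader might infer that 5.1.5.7 removes all progression and leaves the composite unable to show a drug effect. The documents do not support that: only the pooled mean change is lost.

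The percent-slowing rule is attached to the ADAS-cog14 hypothesis, and the hypothesis figure is not available here. Applying it to the composite is an inference from the shared -0.92, which could itself be a benchmark error.

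Pooling is also a reading. The composite text sums across individuals, while 6.6 refers to a group mean. If z-scores were taken within arm, the identity would fail, but the treatment difference would largely vanish.

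The subtraction order may be a slip of wording, since the composite effects quoted in 1.6 are negative. If coded literally, however, observed and carried-forward values would have opposite signs.

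**Conclusion.** Wrong as written, and it should be fixed. The conflict between 1.6 and 5.1.5.7 is plain on the page, and the complete-data result of about -200% follows from algebra once z-scores are pooled. If the footnote is applied to the composite as 5.1.5.7 defines it, the percent-slowing limb cannot separate benefit from harm.

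Two further readings go too far. One is that the ratio is always about -200%: with dropout and LZCF it is unstable rather than constant, and the 69% and 88% rest on assumed item variances, decline and drug effect. The other is that the effect and 49% power in 1.6 are known to belong to baseline scaling. The SAP never says which scaling produced them, and 1.6 itself calls the scores within-visit.

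The damage is limited to a fallback proof-of-concept outcome. The ADAS-cog14 primary analysis is unaffected.

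**What to change.** Before unblinding:

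1. Use one definition in 1.6, 5.1.5.7 and 5.1.5.8: z = (item score at visit x - baseline item mean) / baseline item SD. Take the mean and SD over both arms, hold them fixed for all visits, and let higher mean worse. The GST already uses baseline scaling.
2. Amend LZCF in 6.6 so that carried-forward composite values end on the same baseline scale, and with the same sign, as observed values. Changing the definition alone would mix two scales in the only analysis planned for the composites.
3. State in the Section 2 footnote which outcome the -0.92 and -61% benchmarks apply to, and how -61% was derived.
4. Do not compute percent slowing on any same-visit z-score.
5. Confirm which scaling produced the composite effects and powers in 1.6, and correct the swapped labels.

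The cost is SAP wording and a small change to the derivation and imputation code. No new data are needed.
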